## 9 STATISTICAL CONSIDERATIONS

### 9.1 General Design Issues

The primary and secondary hypotheses is that subjects randomized to the intervention arm will have better control of risk factors and higher rates of adoption of healthy lifestyle habits compared to the control arm.

All outcomes will be collected by a blinded RA. Vascular events will be collected by patient self-report and will not require an adjudication committee.

The design is a RCT, 1:1 allocation to control and intervention arms. There is no crossover.

Randomization is stratified by site (4), language (3: English, Spanish, other), and type of stroke (2: ischemic/TIA, hemorrhagic). There are 24 strata.

Intervention on period is up to 12 months for persons. It may be discontinued if subjects optimally control risk factors.

After the 12 month study period, subjects will be monitored by telephone for the presence of vascular events and mortality. There is no face-to-face contact, and thus, no collection of SBP, the primary endpoint. This surveillance is to better determine the impact of the intervention in the first 12 months after randomization.

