### 9.3 Sample Size and Accrual

#### **Power Analysis**

Power Analyses was conducted with comparison of main outcomes (systolic blood pressure (SBP)) between the control and intervention arms. Based on availability of patients and our capacity, we plan to enroll 500 subjects from four senior centers. Using Intra-class correlation (ICC) of the four centers at 0.0085 level, attrition after the baseline between 20% to 30% level, mean SBP 141 mm Hg and standard deviation (SD) 20, three repeated measurements: baseline, 3 months, and 12 months (Brown and Prescott 2006), the underlying

statistical power of the study comes from two dimensions of observations: the number of unique subjects and the number of repeated measurements within a subject. Based on sample size and power analyses method proposed by Diggle et al. (1994) and Liu et al. (2005) for repeated measures analysis with a type I error of 0.05, type II error of 0.2 (or equivalent to power of 80%), 2.6 and 2.4 average data points for each subject (corresponding to 20% and 30% attrition respectively), and an auto-correlation at 0.2 level, the effective sample size will be 147 and 147 out of the planned 250 and 250 participants in each of the 2 arms (after adjusting for clustering effect), which will enable us to detect an effect size for SBP as small as 0.215 in standard deviation units or 4.29 mm Hg (for 20% attrition), and 0.253 in standard deviation units or 5.06 mm Hg (for 30% attrition).

The seminal work for moderator and mediator effect was from Baron and Kenny (1986). For potential moderators (e.g., age, gender, stroke type and severity, education, country of birth/primary language), we will test power of moderation using the most common measure of effect size  $f^2$  (Aiken & West, 2001), which equals the unique variance explained by the interaction term divided by sum of the error and interaction variances. Cohen (1988) has suggested that  $f^2$  effect sizes of 0.02, 0.15, and 0.35 are termed small, medium, and large, respectively. A more realistic standard for effect sizes with moderators might be 0.005, 0.01, and 0.025 for small, medium, and large, respectively.

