To check the fidelity (uptake) of the SUCCEED intervention, we will also analyze attendance at SUCCEED clinics and the number of telephone coordination of care calls made during enrollment. Because subjects will be recruited from four hospital systems, there could be some underlying intra-site correlations of outcome measures in the collected data, which will have potential impacts on statistical significant tests of parameter estimates in the analyses. To take this into account in our analyses and modeling, robust standard errors will be calculated using Huber/ White/Sandwich method to ensure valid significance testing. Although we will assess for the impact of clustering data structure, we do not expect a large intra-site correlation because the three sites are part of the same county healthcare system and we are not aware of differences of outcomes by site. Furthermore, we will also include site dummies in our model to control and evaluate the differences in parameter estimates, especially if there are significant variations among the sites.

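### Section 9.3 cuts 250 per arm to 147 for clustering by site, although patients are randomised within site, and neither 147 nor the detectable differences follow from the stated inputs

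*Combined protocol and SAP*

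**What the plan says.** The Power Analysis in section 9.3 starts from 500 patients, 250 per arm. Its inputs include "Using Intra-class correlation (ICC) of the four centers at 0.0085 level", "attrition after the baseline between 20% to 30% level" and "mean SBP 141 mm Hg and standard deviation (SD) 20". It also takes a type I error of 0.05, 80% power, a within-patient correlation of 0.2, and an average of 2.6 or 2.4 data points per patient at the two attrition levels. It concludes that "the effective sample size will be 147 and 147 out of the planned 250 and 250 participants in each of the 2 arms", and adds that this is "after adjusting for clustering effect". From there it gives detectable differences of 0.215 SD (4.29 mm Hg) at 20% attrition and 0.253 SD (5.06 mm Hg) at 30%. The last paragraph of 9.3 repeats both figures to conclude that the sample is large enough. The design effect and its formula are not shown.

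On allocation, section 9.1 states: "Randomization is stratified by site (4), language (3: English, Spanish, other), and type of stroke (2: ischemic/TIA, hemorrhagic". Section 4.3.4 specifies 1:1 lists in permuted blocks of 4, one list per stratum. Section 9.5 plans robust standard errors and site indicator terms in the model.

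Two descriptions of the sites conflict with the rest of the document. Section 9.3 says "we plan to enroll 500 subjects from four senior centers", although the sites are county hospitals. Section 9.5 says "we do not expect a large intra-site correlation because the three sites are part of the same county healthcare system", although every other section has four.

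**The concern.** A reduction of this kind belongs to trials that allocate whole sites to one arm. There, a site that runs high or low shifts only one arm, and patients from the same site carry overlapping information about the comparison. Here every site contributes to both arms in equal proportion, so that reasoning does not carry over.

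If the adjustment is misplaced, 9.3 misstates how much information 500 patients provide. If 147 and the two detectable differences cannot be recovered from the listed inputs, the published justification of the sample size cannot be checked, and the adequacy statement that closes 9.3 rests on figures with no visible source.

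**Working it through.** **1. Reproducing 147.** The inputs are 250 per arm and ICC 0.0085 (section 9.3). The formula is not given, so the usual one is assumed: effective n = n / DE, with DE = 1 + (m − 1) × ICC and m the cluster size.

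| Reading | m | DE | Effective n per arm |
|---|---|---|---|
| Four sites, one arm | 250/4 = 62.5 | 1.523 | 164.2 |
| Four sites, both arms | 500/4 = 125 | 2.054 | 121.7 |
| Four sites, one arm, 20% attrition | 200/4 = 50 | 1.417 | 200/1.417 = 141.2 |
| Four sites, one arm, 30% attrition | 175/4 = 43.75 | 1.363 | 175/1.363 = 128.4 |
| Three sites, one arm | 250/3 = 83.33 | 1.700 | 147.07 |

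Unequal site sizes in the proportions of Table 2 move the first row to between 157 and 159. Working backwards, 250/147 = 1.7007 implies m = 1 + 0.7007/0.0085 = 83.4, which is 250/3.

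**2. Whether a site effect belongs in the calculation.** With equal arms within each site, the site effect enters both arm means equally and drops out of the difference:

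Var(difference) = 2 × SD² × (1 − ICC) / n = 2 × 400 × 0.9915 / 250 = 3.17, an SD of 1.78 mm Hg.

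This corresponds to 250/0.9915 = 252 independent patients per arm. A simulation of 20,000 trials (four sites, arms balanced within site, ICC 0.0085, SD 20) gave a variance of 3.14, an SD of 1.77. For comparison, 250 independent patients per arm give √(800/250) = 1.79, and 147 give √(800/147) = 2.33.

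**3. Whether 4.29 and 5.06 mm Hg follow from 147.** The printed text gives no formula here either. The standard one for a mean of k equally correlated measurements is

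difference = 20 × (1.960 + 0.842) × √{2[1 + (k − 1) × 0.2] / (k × n)},

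with a two-sided test assumed because sidedness is not stated.

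- n = 147, k = 2.6: 0.233 SD, 4.66 mm Hg (stated 4.29).
- n = 147, k = 2.4: 0.239 SD, 4.77 mm Hg (stated 5.06).
- One-sided: 0.207 and 0.212 SD, which do not match either.
- The stated 0.253 SD appears at k = 2. The stated 0.215 SD would need k of about 3.4, more than the three measurements planned.

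**4. What the inputs give without the site adjustment.** Attrition is already inside the averages of data points: 1 + 2 × 0.8 = 2.6 and 1 + 2 × 0.7 = 2.4. It must therefore not also reduce n.

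| Analysis | n per arm | 20% attrition | 30% attrition |
|---|---|---|---|
| Repeated-measures formula, k = 2.6/2.4 | 250 | 3.57 mm Hg | 3.66 mm Hg |
| Simple 12-month comparison, SD 20 | 200/175 | 5.60 mm Hg | 5.99 mm Hg |

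**5. Power for the hypothesised 8 mm Hg (section 1.1, Objective 2).** Take 147 per arm and a single endpoint. The standard error is 20 × √(2/147) = 2.33, so 8/2.33 = 3.43, and 3.43 − 1.96 = 1.47, which is about 93% power.

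**The case against.** The strongest defence is that some allowance for clustering may be prudent. Care managers, community health workers, group clinics and classes deliver the intervention, so outcomes in that arm could be correlated within provider, and the treatment effect could differ by site. The enrolment and attrition weights in section 9.5 can also reduce effective sample size. This stands as a caution against treating 250 as exact. It does not support 147: section 9.3 defines its ICC over the centres and argues none of these sources.

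A second defence is that the three-site origin is reverse-engineered. That is fair. One four-site variant comes close: m = 500 × 0.7/4 = 87.5 gives 144.1. But it shrinks the clusters for attrition and leaves the 250 whole, and at 20% attrition it gives 135.8, whereas the plan states one figure for both levels. Three sites is the only coherent exact match found, and section 9.5 makes the same slip. It remains an inference.

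A third is that little depends on the figure. Section 9.3 says that 500 was set by patient availability and capacity, and 147 errs on the cautious side. Both are correct, and they limit the consequence.

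A reader might infer that the inputs were carried over from another project, given the mention of senior centers. One wording slip does not establish that. A reader might also infer that every detectable difference in the plan is about 30% too large, since √(250/147) = 1.30. The documents do not support that: the stated differences do not follow from 147 in the first place, and a simple 12-month comparison gives larger values than the plan states.

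**Conclusion.** The point holds as a correction to the sample size justification. A centre-level ICC gives no reason to reduce 250 per arm when patients are randomised within site and site is in the model. Even on its own terms, the adjustment gives 164 with four sites, not 147. Separately, 4.29 and 5.06 mm Hg are not recovered from 147 and the stated correlation and data points, which give 4.66 and 4.77. Correcting 147 alone would therefore not repair them.

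A reader might infer that the trial is underpowered or that 500 is the wrong number. Neither follows. Replacing 147 raises the effective sample size, and power for 8 mm Hg is about 93% even at 147 with one endpoint. The less favourable recalculation, 5.60/5.99 mm Hg, is also still below 8. It is, however, worse than the plan's 4.29/5.06, so the direction of the change depends on which analysis is named.

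These results assume SD 20, a two-sided 5% test, the standard formulas shown, no variation of the treatment effect between sites, and no provider clustering.

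**What to change.** - In section 9.3, remove the site design effect and the effective sample size of 147 per arm. State 250 randomised per arm.
- Recompute the detectable difference for one named primary analysis, with its formula and sidedness, and count attrition once: either through the average number of data points or through the number of patients with a 12-month value. Section 9.5 lists regression models without naming a repeated-measures one, so the choice has to be made explicitly and the two sections aligned.
- Carry the new figures into the closing paragraph of 9.3.
- Correct the site count in section 9.5 and the description of the hospitals in section 9.3.
- If the sponsor meant to allow for clustering by care manager or community health worker, say so and give that ICC and the assumed caseload.

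The cost is recalculation and text. Enrolment, visits and conduct do not change.

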Due to the low power in tests of moderation, there are greater interests in mediation over moderation (McClelland & Judd, 1993). To analyze power of potential mediators (e.g., self-efficacy, self-management, social isolation, depression, perceived risk of stroke), we will use indirect effect, which is the product of coefficient from independent variable to mediator, and mediator to the outcome. Because an indirect effect is a product of two effects, the usual Cohen (1988) standards of .1 for small, .3 for medium, and .5 values should be squared. Thus, a small effect size would be .01, medium would .09, and large would be .25 (or we can use small .02, medium .15, and large .40.)

The effect size for SBP as small as 0.215 in standard deviation units or 4.29 mm Hg (for 20% attrition), and 0.253 in standard deviation units or 5.06 mm Hg (for 30% attrition) can be considered clinically meaningful in the present of both moderators and mediators. Thus, the planned sample size should be sufficient for analyses.

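### Section 9.3 infers that the sample suffices with moderators and mediators from the SBP main effect alone; at the plan's own more realistic sizes, small and medium moderators are underpowered, as are small mediated effects

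*Combined protocol and SAP*

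**What the plan says.** The Power Analysis in section 9.3 reports one kind of numerical result: the SBP difference between arms detectable with 80% power, 0.215 SD (4.29 mm Hg) at 20% attrition and 0.253 SD (5.06 mm Hg) at 30%.

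For moderators it lists Cohen's f2 values (0.02, 0.15, 0.35) and then adds: "A more realistic standard for effect sizes with moderators might be 0.005, 0.01, and 0.025 for small, medium, and large, respectively". For mediators it gives a separate scale for the indirect effect: 0.01, 0.09 and 0.25, or alternatively 0.02, 0.15 and 0.40. It states no power, required sample size or detectable effect for either. Between the two it concedes that power for moderation is low and says interest therefore shifts to mediation.

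The closing paragraph returns to the 4.29 and 5.06 mm Hg figures, says they "can be considered clinically meaningful in the present of both moderators and mediators", and ends: "Thus, the planned sample size should be sufficient for analyses".

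Section 1.1 places moderator and mediator analysis within Primary Objective #2, with moderators examined to judge how robust the intervention's effect is across patient and system characteristics. Section 9.5 tests moderators by likelihood ratio tests of interaction terms, and mediators by the Baron and Kenny steps with Sobel and bootstrap tests.

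**The concern.** The conclusion does not follow from its premise. The precision of a difference between two arms does not give the precision of a difference between two such differences, nor of a product of two regression paths. The conclusion also sits badly with the low moderation power admitted a few lines earlier.

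At stake is what the trial can say about robustness under Primary Objective #2. If an interaction test has even odds or worse of detecting an effect the plan calls medium, a non-significant result is weak evidence that the effect is uniform. A protocol that calls the sample sufficient invites the opposite reading.

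**Working it through.** **Inputs.** From section 9.3: 500 enrolled, 250 per arm; "attrition after the baseline between 20% to 30% level", so 400 or 350 analysed; alpha 0.05 and power 80%; SD 20 mm Hg; effective 147 per arm after clustering; 2.6 or 2.4 data points per subject; auto-correlation 0.2; the moderator and mediator benchmarks above. From section 1.1: a hypothesised SBP effect of 8 mm Hg. Assumed, because not stated: two-sided tests, no multiplicity correction, and one outcome time (section 9.5 names linear and ordinal logistic regression, not a repeated-measures model).

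**1. The plan's own figure.** Detectable effect = (1.960 + 0.842) × sqrt(2/n), with n = 147m/[1 + (m − 1) × 0.2].
- m = 2.6: n = 382.2/1.32 = 289.5, giving 0.233 SD (4.66 mm Hg); stated 0.215.
- m = 2.4: n = 352.8/1.28 = 275.6, giving 0.239 SD (4.77 mm Hg); stated 0.253.

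The stated values appear only with whole data points under first-order autoregression: m = 3 gives 9/3.88 = 2.32 effective points and 0.2146 SD; m = 2 gives 4/2.4 = 1.67 and 0.2531 SD. Likewise 147 appears with three sites, 250/[1 + (83.3 − 1) × 0.0085] = 147.1; four sites give 164.2. These mismatches are a separate matter. What counts here is that the formula contains only the two arm means and no interaction or indirect effect.

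**2. Moderators.** Noncentral F test of one interaction term: 1 and N − 4 df, noncentrality f2 × N.

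| N analysed | f2 0.005 | f2 0.01 | f2 0.025 |
|---|---|---|---|
| 400 (20% attrition) | 29% | 51% | 88% |
| 350 (30% attrition) | 26% | 46% | 84% |
| 500 (no attrition) | 35% | 61% | 94% |

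For 80% power the required N is 1,572, 787 and 316. The f2 detectable with 80% power is 0.0197 at N = 400 and 0.0226 at N = 350. Section 9.3 defines f2 with the interaction variance also in the denominator; converting by f2/(1 − f2) moves power by at most about 1 point.

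**3. Sensitivity.**
- Repeated-measures credit on 147 per arm: 2 × 289.5 = 579 or 2 × 275.6 = 551, giving 38-40% (small), 65-67% (medium) and 96-97% (large).
- Full repeated-measures credit with no loss to attrition or clustering (N about 938-985): medium reaches 86-88%, small 58-60%.
- More than 1 df, N = 350-400: with 2 df, 20-22%, 37-41% and 75-81%; with 3 df, 17-19%, 31-36% and 69-76%. Language in the plan's three strata is a 2-df moderator.

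**4. In mm Hg.** With a moderator split 50/50, an interaction of D explains D²/16 of the variance. For D = 8: 64/16 = 4, and 4/20² = 0.01, the plan's medium. So if one half of patients gained 8 mm Hg more than the other, the test would miss it about half the time. The detectable interaction is 2.80 × 20 × sqrt(16/N) = 11.2 mm Hg (N = 400) or 12.0 (N = 350). For stroke type, Table 2 gives 188 + 211 + 197 = 596 hemorrhagic of 1,075 + 1,144 + 1,088 = 3,307 admissions, or 18%. If enrolment matched that, 2.80 × 20 × sqrt[4/(N × 0.18 × 0.82)] = 14.6 to 15.6 mm Hg.

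**5. Mediators.** Two equal standardised paths, each the square root of the indirect effect, N = 350-400; power by simulation (4,000 runs), with a product-of-powers check for joint significance.

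| Indirect effect | Joint significance | Sobel |
|---|---|---|
| 0.01 | 22-27% | 7-9% |
| 0.02 | 56-66% | 33-42% |
| 0.09 and above | about 100% | about 100% |

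**The case against.** The strongest reply is that the closing sentence does not say which analyses it covers, that the figure before it is a main effect, and that the plan openly concedes low moderation power and gives moderation less weight. This stands in part. A reader might infer that the plan makes a plainly false claim of adequate power for moderators and mediators, but the text is not specific enough for that. What it supports is narrower: in a paragraph about moderators and mediators, sufficiency is inferred from a figure that does not bear on them, against a concession just made.

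A reader might also carry the 26-29% and 46-51% over to mediators. The documents do not support this: mediators have their own, larger benchmarks, and only the small ones fall short.

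A third tempting step is to treat 2 × 147 = 294 as the final information size. Section 9.3 describes 147 as adjusted for clustering and counts repeated measurements as a further source of power. On its own, 147 per arm would give 2.80 × sqrt(2/147) = 0.327 SD, not the plan's figures.

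Two more points are fair. Section 9.3 also lists Cohen's small f2 of 0.02, at which power is about 75% (N = 350) to 81% (N = 400), and it says only that the smaller set might be more realistic. And nowhere does the plan state that a non-significant interaction will be read as robustness; that is a risk, not a stated rule. Neither point supplies the missing calculation or brings the plan's more realistic small and medium moderators to 80% under attrition and clustering.

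**Conclusion.** The sufficiency statement is unsupported for moderator and mediator analyses and in conflict with the same section's concession. No stated moderator or mediator figure is miscalculated, because none is stated.

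At the more realistic sizes, moderator power is about 26-29%, 46-51% and 84-88% for small, medium and large. This assumes 1 df, two-sided alpha 0.05, the 12-month outcome alone, no multiplicity correction and 350 to 400 analysed. Large moderators are therefore adequately covered under those assumptions. Small and medium ones are not, including with repeated-measures credit on the plan's clustering-adjusted sample; medium passes 80% only if attrition and clustering are both ignored. Additional degrees of freedom, or correction for the many moderators listed, would lower these figures. For mediators the shortfall is confined to small indirect effects, assuming equal paths.

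The main-effect comparison is not called into question by this point. What is limited is the conclusion about robustness that Primary Objective #2 can draw.

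**What to change.** Replace the last sentence of section 9.3 with a statement to this effect:

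> The sufficiency of the sample refers to the main effect on SBP. For a single 1-df moderator of the 12-month outcome, two-sided alpha 0.05 and no multiplicity correction, 80% power requires f2 of about 0.020 (400 analysed) to 0.023 (350 analysed); moderators with more degrees of freedom require larger effects. Small and medium moderators (f2 0.005 and 0.01) and small indirect effects (0.01 to 0.02) are underpowered. Moderator and mediator analyses are exploratory and will be reported as estimates with 95% confidence intervals. A non-significant interaction will not be taken as evidence that the effect is robust across subgroups.

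Sections 1.1 and 9.5 should carry the same exploratory label. The cost is wording only: a stated property of the design becomes less favourable. No patients, visits or procedures are added.

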#### **9.4 Data Monitoring**

For Care Management studies such as this proposed study, a Data Safety Monitoring Board (DSMB) is not usually required. However, should NINDS require a DSMB, we will establish an Internal DSMB for this minimal risk study. Care coordinators will be monitoring risk factor control and resource utilization of subjects randomized to the intervention. Care coordinators will be making multiple telephone calls about coordination of care. They will ask subjects about the steps they are taking to lower the risk of stroke.

#### **ClinicalTrials.gov Requirements**

This trial does not meet the FDAAA requirement for mandated registration in ClinicalTrials.gov because it does not involve a drug, biologic, or device. However, we do plan to register this trial on ClinicalTrials.gov. Such registration is required for findings to be published in many medical journals, and it could also serve to enhance the dissemination of the trial's results.

